#### 9.2.2. Sample Size Sensitivity

For a sensitivity analysis, assuming a range of within-subject variability, a sample size of 12 evaluable subjects, it is estimated that the precision (i.e., half-width of the 90% CI on the log and ratio scale), and CI on the original scale for each PE will be as follows:

		Half-Width	Half-Width		
Drug	CVw (%)	(log scale)	(original scale)	Point Estimate	90% CI
TAF/FTC or	10	0.073	0.076	0.9	(0.837, 0.968)
GSK3640254				1.0	(0.930, 1.076)
				1.1	(1.023, 1.183)
				1.2	(1.116, 1.291)
	20	0.145	0.156	0.9	(0.779, 1.040)
				1.0	(0.865, 1.156)
				1.1	(0.952, 1.272)
				1.2	(1.038, 1.387)
	30	0.215	0.240	0.9	(0.726, 1.116)
				1.0	(0.807, 1.240)
				1.1	(0.887, 1.364)
				1.2	(0.968, 1.488)
	40	0.283	0.327	0.9	(0.678, 1.194)
				1.0	(0.754, 1.327)
				1.1	(0.829, 1.460)
				1.2	(0.904, 1.593)

Approximately 16 participants will be treated to ensure that 12 evaluable participants complete the study.

# 9.3. Populations for Analyses

Population	Description
Screened	All participants who sign the ICF.
Safety	All participants who receive at least 1 dose of study medication. This population will be used for all demographic and safety summaries.
Pharmacokinetic Concentration	The PK Concentration Population will include all participants who undergo plasma PK sampling and have evaluable PK assay results. This population will be used for the concentration listing.
Pharmacokinetic Parameter	The PK Parameter Population will include all participants who undergo plasma PK sampling and have evaluable PK parameters estimated. This population will be used for PK parameter listing, plotting of the concentration-time data and PK parameter summary.

For purposes of analysis, the following populations are defined:

# 9.4. Statistical Analyses

#### 9.4.1. Pharmacokinetic Analyses

Plasma GSK3640254 and TAF, FTC, and TFV concentration-time data will be analyzed by PPD, under the oversight of Clinical Pharmacology Modeling & Simulation department within GSK, using noncompartmental methods with Phoenix WinNonlin Version 6.4 or higher. Statistical analysis will be performed by PPD, under the oversight of Clinical Statistics, GSK. Calculations will be based on the actual sampling times recorded during the study.

Endpoint	Statistical Analysis Methods
Primary	• The primary endpoints of this study are PK-related. The analysis for the primary PK endpoints will be performed for the PK Parameter Population. Plasma concentrations of TAF, FTC, and TFV will be subjected to PK analyses using noncompartmental methods.
	
 
Based on the individual concentration-time data the following primary plasma parameters will be estimated:
 

	
 
TAF (Periods 1 and 2): AUC(0-τ) and Cmax
 

	
 
FTC and TFV (Periods 1 and 2): AUC(0-τ), Cmax, and Cτ
 

	
 
Analyses will be performed to assess the effect of GSK3640254 on the PK of TAF, FTC, and TFV, as appropriate. Analyses will be performed on the natural logarithms of AUC(0-τ), Cτ, and Cmax using linear mixed-effect models with treatment as a fixed effect and subject as a random effect. Effects will be estimated, and CIs will be constructed for the following treatment comparison:
 

	Period 2 versus Period 1
	
 
Point estimates and 90% CIs for treatment differences on the log scale derived from the model will be exponentiated to obtain estimates for geometric mean ratios and CIs on the original scale.
 

	
 
Summary statistics (arithmetic mean, geometric mean, median, standard deviation, minimum, maximum, and coefficient of variation) for plasma TAF, FTC, and TFV PK parameter values will be summarized by study day.
 

Secondary	
 
Plasma concentrations of GSK3640254 will be subjected to PK analyses using noncompartmental methods.
 

	
 
Based on the individual concentration-actual time data the following secondary plasma parameters will be estimated:
 

	
 
TAF, FTC, and TFV (Periods 1 and 2): Tmax
 

	
 
GSK3640254 (Period 2): AUC(0-τ), Cmax, Cτ, and Tmax (note: GSK3640254 PK parameter values in the presence of TAF/FTC from this study will be compared with GSK3640254 PK parameter values from previous studies)
 

	
 
Summary statistics (arithmetic mean, geometric mean, median, standard deviation, minimum, maximum, and coefficient of variation) for plasma GSK3640254 and TAF, FTC, and TFV PK parameter values will be summarized by study day.
 

	
 
Additionally, predose (trough) PK plasma concentrations (TAF, FTC, and TFV: Days 2 through 14 [Period 1] and 1 through 7 [Period 2]; GSK3640254: Days 2 through 7 [Period 2]) will be summarized using the PK Concentration Population, and used to assess achievement of steady state.
 

Exploratory	Will be described in the reporting and analysis plan

# 9.4.2. Safety Analyses

All safety analyses will be performed on the Safety Population.

Safety data will be presented in tabular format and summarized descriptively according to GSK's Integrated Data Standards Library (IDSL) standards. No formal statistical analysis of the safety data will be conducted.

The details of the statistical analyses of safety and PK data will be provided in the reporting and analysis plan.

# 9.4.3. Other Analyses

Not applicable.

#### 9.5. Interim Analyses

No interim analysis is planned.

# 9.5.1. Data Monitoring Committee (DMC)

Not applicable.

# 10. SUPPORTING DOCUMENTATION AND OPERATIONAL CONSIDERATIONS

# **10.1.** Appendix 1: Abbreviations and Trademarks

AE	Adverse event
ALT	Alanine aminotransferase
AST	Aspartate aminotransferase
AUC	Area under the plasma concentration-time curve
AUC(0-∞)	Area under the plasma concentration-time curve from time zero extrapolated to infinity
ΑUC(0-τ)	Area under the plasma concentration-time curve from time 0 to the end of the dosing interval at steady state
AUC(0-24)	Area under the plasma concentration-time curve from time 0 to 24 hours after dosing
BMI	Body Mass Index
BMS	Bristol-Myers Squibb
CA	Competent Authorities
cDNA	Complementary Deoxyribonucleic acid
CFR	Code of Federal Regulations
CI	Confidence interval
CIB	Clinical Investigator's Brochure
Cmax	Maximum observed concentration
CONSORT	Consolidated Standards of Reporting Trials
СРК	Creatine phosphokinase
CRF	Case report form
C-SSRS	Columbia-Suicide Severity Rating Scale
Cτ	Plasma concentration at the end of the dosing interval
CV	Cardiovascular
CVw	Intra-subject coefficient of variation
CYP	Cytochrome P450
DAIDS	Division of AIDS
DDI	Drug-drug interaction
EC	Ethics Committee
ECG	Electrocardiogram
FSH	Follicle-stimulating hormone
FTC	Emtricitabine
FTIH	First-time-in-human
GCP	Good Clinical Practice
	•

GIGastrointestinalGSKGlaxoSmithKlineIC50Half maximal inhibitory concentrationHBsAgHepatitis B surface antigenHDPEHigh-density PolyethyleneHIPPAHealth Insurance Portability and Accountability ActHIVHuman immunodeficiency virusHRTHormonal replacement therapyICFInformed consent formICHInternational Council for HarmonisationIDSLIntegrated Data Standards LibraryIECIndependent Ethics Committee		
IC50Half maximal inhibitory concentrationHBsAgHepatitis B surface antigenHDPEHigh-density PolyethyleneHIPPAHealth Insurance Portability and Accountability ActHIVHuman immunodeficiency virusHRTHormonal replacement therapyICFInformed consent formICHInternational Council for HarmonisationIDSLIntegrated Data Standards Library		
HBsAgHepatitis B surface antigenHDPEHigh-density PolyethyleneHIPPAHealth Insurance Portability and Accountability ActHIVHuman immunodeficiency virusHRTHormonal replacement therapyICFInformed consent formICHInternational Council for HarmonisationIDSLIntegrated Data Standards Library		
HDPEHigh-density PolyethyleneHIPPAHealth Insurance Portability and Accountability ActHIVHuman immunodeficiency virusHRTHormonal replacement therapyICFInformed consent formICHInternational Council for HarmonisationIDSLIntegrated Data Standards Library		
HIPPAHealth Insurance Portability and Accountability ActHIVHuman immunodeficiency virusHRTHormonal replacement therapyICFInformed consent formICHInternational Council for HarmonisationIDSLIntegrated Data Standards Library		
HIVHuman immunodeficiency virusHRTHormonal replacement therapyICFInformed consent formICHInternational Council for HarmonisationIDSLIntegrated Data Standards Library		
HRTHormonal replacement therapyICFInformed consent formICHInternational Council for HarmonisationIDSLIntegrated Data Standards Library		
ICF       Informed consent form         ICH       International Council for Harmonisation         IDSL       Integrated Data Standards Library		
ICH     International Council for Harmonisation       IDSL     Integrated Data Standards Library		
IDSL Integrated Data Standards Library		
, , , , , , , , , , , , , , , , , , ,		
IgM Immunoglobulin M		
INR International normalized ratio		
IRB Institutional Review Board		
LDH Lactate dehydrogenase		
	Multiple-ascending dose	
µg Micrograms		
mg Milligrams		
MI Maturation inhibitor		
MRP Multi-drug resistance protein		
OATP Organic anion-transporting polypeptide		
PE Point estimate		
PK Pharmacokinetic(s)		
QD Once daily		
QTc Corrected QT interval		
QTcF Fridericia QT correction formula		
SAD Single-ascending dose		
SAE Serious adverse event		
SoA Schedule of activities		
SRM Study Reference Manual		
SUSAR Suspected unexpected serious adverse reactions		
t1/2 Terminal phase half-life		
TAF/FTC Tenofovir alafenamide/emtricitabine		
TFV Tenofovir		
Tmax         Time of maximum observed concentration		
TQT Thorough QT	Thorough QT	
UGT Uridine diphosphate glucuronosyltransferase		

ULN	Upper limit of normal
US	United States
USPI	United States Prescribing Information
VH	ViiV Healthcare
WOCBP	Woman of childbearing potential

# **Trademark Information**

Trademarks of ViiV Healthcare	
NONE	

Trademarks not owned by the ViiV Healthcare	

DAIDS DESCOVY

# **10.2.** Appendix 2: Clinical Laboratory Tests

- The tests detailed in Table 2 will be performed by the local laboratory.
- Protocol-specific requirements for inclusion or exclusion of participants are detailed in Section 5 of the protocol.
- Additional tests may be performed at any time during the study as determined necessary by the investigator or required by local regulations.
- Pregnancy Testing
  - Refer to Section 5.1 Inclusion Criteria for screening pregnancy criteria.
  - Pregnancy testing (urine or serum as required by local regulations) should be conducted at the time points indicated in the SoA (Section 1.3).
  - Additional serum or urine pregnancy tests may be performed, as determined necessary by the investigator or required by local regulation, to establish the absence of pregnancy at any time during the participant's participation in the study.

Laboratory Assessments	Parameters			
Hematology	Platelet Count Red Blood Cell Count Hemoglobin Hematocrit	Red Blood Cell Indices: Mean corpuscular volume Mean corpuscular hemoglobin	White blood cell count with differential:NeutrophilsLymphocytesMonocytesEosinophilsBasophils	
Clinical Chemistry ¹	Blood urea nitrogen	Aspartate aminotransferase	Globulin	
	Creatinine	Alanine aminotransferase	Anion gap	
	Glucose (fasting) Potassium	Gamma-glutamyl transferase Total and direct bilirubin	Alkaline phosphatase Uric acid	
	Sodium	Lactate dehydrogenase	Creatine phosphokinase	
	Calcium	Total cholesterol	Serum lipase	
	Chloride	Triglycerides	Serum amylase	
	Phosphorus	Total protein		
	Carbon dioxide	Albumin		
Routine Urinalysis	
 
Specific gravity
 
pH, glucose, protein, blood, ketones, bilirubin, urobilinogen, nitrite, and leukocyte esterase by dipstick
 
Microscopic examination (if blood, leukocyte esterase, or protein is abnormal)
 
			

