### 5.2. Baseline Definitions

For all endpoints (except as noted in baseline definitions), the baseline value will be the latest pre-dose assessment with a non-missing value, including those from unscheduled visits. If time is not collected, Day 1 assessments are assumed to be taken prior to first dose and used as baseline. Baseline is applied to each treatment period.

Parameter	Study As	sessment Basel	s Considered as ine	Baseline Used in Data Display					
	Screening	Day -1	Day 1 (Pre-Dose)	Period 1 Period 2					
Safety									
Vital Sign	Х	Х	X	Day 1 (Pre-Dose) for each period					
12-Lead ECG	Х	Χ	Х	Day 1 (Pre-Dose)[1] for each period					
Hematology	Х	Х		Day -1 Period 1 Day 14					
Clinical Chemistry	Х	Х		Day -1 Period 1 Day 14					
Urinalysis	Х	Χ		Day -1	Period 1 Day 14				

 The average (for quantitative assessments) or the worst case (for interpretation) of the predose triplicate assessments on Day 1 of Period 1 will be used as the baseline for Period 1. The average (for quantitative assessments) or the worst case (for interpretation) of the predose triplicate assessments on Day 1 of Period 2 will be used as the baseline for Period 2.

Unless otherwise stated, if baseline data is missing no derivation will be performed and baseline will be set to missing.

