# 10.6. Appendix 6: Division of AIDS (DAIDS) Table for Grading the Severity of Adult and Pediatric Adverse Events

## 10.6.1. Laboratory Values

Laboratory abnormalities will be graded according to the DAIDS grading table Version 2.1, July 2017. Laboratory results are converted to use SI units; only the numeric part of the criteria will be used. If for a laboratory parameter there are multiple grades sharing the same criteria, the maximum grade will be used.

HEMATOLOGY				
	Grade 1	Grade 2	Grade 3	Grade 4
Absolute Lymphocyte Count, Low (cell/mm³; cells/L) > 5 years of age (not HIV infected)	600 to < 650 0.600 × 10  to < 0.650 × 10 	500 to < 600 0.500 × 10  to < 0.600 × 10 	350 to < 500 0.350 × 10  to < 0.500 × 10 	< 350 < 0.350 × 10 
Absolute Neutrophil Count, Low (cells/mm³; cells/L) > 7 days of age	800 to 1,000 0.800 × 10  to 1.000 × 10 	600 to 799 0.600 × 10  to 0.799 × 10 	400 to 599 0.400 × 10  to 0.599 × 10 	< 400 < 0.400 × 10 
Hemoglobin, Low (g/dL; mmol/L)	10.0 to 10.9	9.0 to < 10.0	7.0 to < 9.0	< 7.0
≥ 13 years of age (male only)	6.19 to 6.76	5.57 to < 6.19	4.34 to < 5.57	<4.34
Hemoglobin, Low (g/dL; mmol/L)	9.5 to 10.4	8.5 to < 9.5	6.5 to < 8.5	< 6.5
≥ 13 years of age (female only)	5.88 to 6.48	5.25 to < 5.88	4.03 to < 5.25	< 4.03
Platelets, Decreased (cells/mm³; cells/L)	100,000 to < 125,000 100.000 × 10  to < 125.000 × 10 	50,000 to < 100,000 50.000 × 10  to < 100.000 × 10 	25,000 to < 50,000 25.000 × 10  to < 50.000 × 10 	< 25,000 < 25.000 × 10 
White Blood Cell, Decreased (cells/mm³; cells/L) > 7 days of age	2,000 to 2,499 2.000 × 10  to 2.499 × 10 	1,500 to 1,999 1.500 × 10  to 1.999 × 10 	1,000 to 1,499 1.000 × 10  to 1.499 × 10 	< 1,000 < 1.000 × 10 

Clinical Chemistry				
	Grade 1	Grade 2	Grade 3	Grade 4
Albumin Low (ald : all )	3.0 to < LLN	≥ 2.0 to < 3.0	< 2.0	NA
Albumin, Low (g/dL; g/L)	30 to < LLN	≥ 20 to < 30	< 20	NA

Clinical Chemistry				
	Grade 1	Grade 2	Grade 3	Grade 4
Alkaline Phosphatase, High	1.25 to < 2.5 × ULN	2.5 to < 5.0 × ULN	5.0 to < 10.0 × ULN	≥ 10.0 × ULN
Alanine Aminotransferase, High	1.25 to < 2.5 × ULN	2.5 to < 5.0 × ULN	5.0 to < 10.0 × ULN	≥ 10.0 ULN

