Sodium, High (mEq/L; mmol/L)	146 to < 150	150 to < 154	154 to < 160	≥ 160
Codium Lourine Fall Lourine (III)	130 to < 135	125 to < 130	121 to < 125	≤ 120
Sodium, Low (mEq/L; mmol/L)	130 to < 135	125 to < 130	121 to < 125	≤ 120
Usia Aaid High (mEa/L, mmal/L)	7.5 to < 10.0	10.0 to < 12.0	12.0 to < 15.0	≥ 15.0
Uric Acid, High (mEq/L; mmol/L)	0.45 to < 0.59	0.59 to < 0.71	0.71 to < 0.89	≥ 0.89

NA=not applicable; LLN = lower limit of normal; ULN=upper limit of normal.

Urinalysis				
	Grade 1	Grade 2	Grade 3	Grade 4
Glucose/Glycosuria (random collection tested by dipstick)	Trace to 1+ or ≤ 250 mg	2+ or > 250 to ≤ 500 mg	> 2+ or > 500 mg	NA
Protein/Proteinuria (random collection tested by dipstick)	1+	2+	3+ or higher	NA
Red Blood Cells (RBCs)/Hematuria (not to be reported based on dipstick findings or on blood believed to be of menstrual origin)	6 to < 10 RBCs per high power field	≥ 10 RBCs per high power field	Gross, with or without clots OR with RBC casts OR intervention indicated	Life-threatening consequences

NA=not applicable

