## 10.9.5. Safety Tables

Safety:	Tables				
No.	Population	IDSL / Example Shell	Title	Programming Notes	Deliverable [Priority]
Advers	e Events (AEs)			•	
2.1.	Safety	AE1CP	Summary of Adverse Events by System Organ Class and Preferred Term		SAC
2.2.	Safety	AE1CP	Summary of Drug-Related Adverse Events by System Organ Class and Preferred Term		SAC
2.3.	Safety	AE3	Summary of Common (>=5%) Adverse Events by Overall Frequency		SAC
2.4.	Safety	AE15	Summary of Common (>=5%) Non-serious Adverse Events by System Organ Class and Preferred Term (Number of Subjects and Occurrences)		SAC
2.5.	Safety	AE16	Summary of Serious Adverse Events by System Organ Class and Preferred Term (Number of Subjects and Occurrences)		SAC
2.6.	Safety	AE5A	Summary of Adverse Events by System Organ Class and Preferred Term and Maximum Intensity		SAC
Labora	tory: Chemistry	/			•
2.7.	Safety	LB1	Summary of Clinical Chemistry Changes from Baseline		SAC
2.8.	Safety	LB16	Summary of Clinical Chemistry Results by Maximum Grade Increase Post-Baseline Relative to Baseline		SAC
Labora	tory: Hematolo	gy		•	
2.9.	Safety	LB1	Summary of Hematology Changes from Baseline		SAC
2.10.	Safety	LB16	Summary of Hematology Results by Maximum Grade Increase Post-Baseline Relative to Baseline		SAC

Safety: Tables						
No.	Population	IDSL / Example Shell	Title	Programming Notes	Deliverable [Priority]	
Labora	tory: Urinalysis	,				
2.11.	Safety	UR3	Summary of Urinalysis Dipstick Results		SAC	
2.12.	Safety	LB1	Summary of Urine Concentration Changes from Baseline		SAC	
2.13.	Safety	LB16	Summary of Urinalysis by Maximum Grade Increase Post- Baseline Relative to Baseline		SAC	
ECG						
2.14.	Safety	EG1	Summary of ECG Findings		SAC	
2.15.	Safety	EG2	Summary of ECG Changes from Baseline		SAC	
2.16.	Safety	EG10	Summary of Maximum QTc Values Post-Baseline Relative to Baseline by Category		SAC	
2.17.	Safety	EG11	Summary of Maximum Increase in QTc Values Post-Baseline Relative to Baseline by Category		SAC	
Vital Si	gns					
2.18.	Safety	VS1	Summary of Vital Sign Changes from Baseline		SAC	
C-SSR	S					
2.19.	Safety	CSSRS4	Listing of C-SSRS Suicidal Ideation and Behavior Data	Only include participants who have suicidal ideation or behavior	SAC	

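### The haematuria line of SAP Table 2.13 omits new haematuria after clean pre-dose urine, because microscopy is a reflex test and a missing baseline is not derived (unless the LB16 shell provides otherwise)

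*Protocol*

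**What the plan says.** - **When microscopy is done.** Protocol Appendix 2, Table 2, lists it under routine urinalysis as a conditional item: "Microscopic examination (if blood, leukocyte esterase, or protein is abnormal"). A clean dipstick therefore produces no cell count.
- **How haematuria is graded.** In the urinalysis table of SAP 10.6.1, Grade 1 is "6 to < 10 RBCs per high power field" and Grade 2 is 10 or more. The row carries the note "not to be reported based on dipstick findings or on blood believed to be of menstrual origin". For laboratory grading in general, "only the numeric part of the criteria will be used", so the descriptive Grade 3 and 4 entries for haematuria offer no other route to a grade.
- **What baseline is.** SAP 5.2 says "the baseline value will be the latest pre-dose assessment with a non-missing value, including those from unscheduled visits". For urinalysis its table allows Screening and Day -1, displays Day -1 for Period 1, and names Period 1 Day 14 for Period 2.
- **What happens without one.** SAP 5.2: "Unless otherwise stated, if baseline data is missing no derivation will be performed and baseline will be set to missing".
- **The display.** SAP 10.9.5, Table 2.13, is the "Summary of Urinalysis by Maximum Grade Increase" post-baseline relative to baseline, on shell LB16. Its programming-notes cell is empty.

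Neither document says what grade to give when microscopy was not triggered.

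**The concern.** In a reflex test, an absent result carries information: dipstick blood, leukocyte esterase and protein were all normal, so nobody needed to look further. The SAP has no rule that recognises this. Its only rule for an absent baseline is to stop, which suits a lost sample but not a test left undone because the urine was clean.

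The consequence runs the wrong way for a safety table. A shift table exists to show participants who were normal before dosing and abnormal afterwards. Here the haematuria line would be built from participants with some pre-dose urine abnormality and would leave out the change from normal.

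Change from baseline in laboratory assessments is part of a secondary endpoint, and Protocol 4.2 describes TAF and FTC as mainly renally excreted. A graded urine summary that compares the two treatments should therefore be right. No pharmacokinetic result depends on it.

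**Working it through.** The plan states no figure on this point, so there is nothing to reproduce. The check traces example participants through the written rules.

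**Rules**

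1. Cell count at a visit = observed value if dipstick blood, leukocyte esterase or protein is abnormal; otherwise none (Protocol Appendix 2).
2. Grade = 0 if the count is below 6, 1 if it is 6 to below 10, 2 if it is 10 or more; no count gives no grade (SAP 10.6.1).
3. Baseline grade = grade from the latest pre-dose visit that has a count (SAP 5.2).
4. Increase = highest post-baseline grade minus baseline grade; no baseline, no derivation (SAP 5.2, Table 2.13).

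**Period 1 examples** (counts of 1 and 15 per high power field are assumed, for illustration)

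| Screening | Day -1 | On treatment | Baseline grade | Highest later grade | Increase as written | Increase with the fix |
|---|---|---|---|---|---|---|
| clean | clean | blood positive, 15 | none | 2 | not derived | 2 - 0 = 2 |
| leukocyte esterase positive, 1 | clean | blood positive, 15 | 0 | 2 | 2 - 0 = 2 | 2 - 0 = 2 |
| clean | blood positive, 15 | blood positive, 15 | 2 | 2 | 2 - 2 = 0 | 2 - 2 = 0 |
| clean | clean | clean throughout | none | none | not derived | 0 - 0 = 0 |

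Rows 1 and 2 have the same on-treatment event. Row 2 is counted only because an unrelated dipstick finding at Screening happened to trigger microscopy. Row 4 shows that participants who stay clean also leave the line, so its denominator is affected as well as its numerator.

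**Period 2.** Baseline is reset to Period 1 Day 14. A clean dipstick that day gives the same result as row 1, unless the general latest-non-missing rule is allowed to reach back to an earlier triggered microscopy. SAP 5.2 does not settle which of the two governs.

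**Scale.** One omitted participant is 1/16 = 6.25% of those treated, or 1/12 = 8.3% of the evaluable target. This shows only what one case weighs; it does not estimate how many there would be.

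**The case against.** **The shell may already deal with it.** Laboratory displays follow the sponsor's standards, and the missing-baseline rule opens with an exception for anything stated elsewhere. LB16 is not in the documents. If it treats a missing baseline as Grade 0, the omission does not occur. This stands, and it makes the conclusion conditional. It does not remove the point, because nothing in either document states the exception.

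**The value may not be missing.** SAP 10.5.2 describes missing data as data that were requested but not supplied, and microscopy was never requested after a clean dipstick. That is a fair reading, but then no rule applies at all and there is still no baseline grade.

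**The fix seems to use the dipstick after the SAP has ruled it out.** The SAP note bars reporting haematuria from a dipstick. Taking a clean dipstick as no haematuria is a different step and does not conflict with it. Equally, nothing in the SAP currently authorises that step, so it has to be written down.

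**Some baselines will exist.** Screening and unscheduled pre-dose visits count, and Appendix 2 lets the investigator add tests. This helps individual participants but does not supply baselines systematically.

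**The practical weight is low.** Participants are healthy, kidney disease is excluded, and Grade 2 to 4 laboratory abnormalities at Screening are generally excluded. The GSK3640254 risks the protocol names are gastrointestinal, QTc and neuropsychiatric, and renal excretion of TAF/FTC does not itself imply haematuria. The number of affected cases may well be zero. All of this stands and keeps the point minor.

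**Conclusion.** The point holds as a minor error in one descriptive line. As written, the haematuria line of Table 2.13 can show a grade increase only for participants with a pre-dose cell count. New haematuria after clean urine is omitted unless LB16 supplies a Grade 0 baseline.

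Three stronger conclusions that a reader might draw are not supported:

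- **That the participant disappears from Table 2.13.** Glucose and protein are graded by dipstick, so those lines have baselines and are unaffected.
- **That the finding is lost from the report.** Listings 24 and 25 cover urinalysis toxicities and do not depend on a baseline grade. Table 2.11 shows the dipstick blood result. Protocol 8.2.4 also has clinically relevant laboratory changes recorded as adverse events.
- **That a known share of cases is missed.** If 5% to 25% of participants had an abnormal baseline dipstick, one could write 1 - 0.25 = 75% to 1 - 0.05 = 95% uncounted. The documents give no dipstick rate. The sum also takes later haematuria to be independent of baseline status and uses a single dipstick occasion, although Screening and Day -1 both qualify. No percentage should be attached.

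The conclusion rests on two assumptions: that LB16 does not fill in the baseline, and that microscopy is not routinely added before dosing.

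**What to change.** Add one rule to SAP 5.2 and 10.6.1: where microscopy was not triggered because dipstick blood, leukocyte esterase and protein were all normal, the urine red-cell grade at that time point, baseline or post-baseline, is Grade 0 for Table 2.13. Base the haematuria line on all participants with a urinalysis at baseline and post-baseline, and repeat the rule in the programming notes for Table 2.13. If LB16 already does this, a sentence saying so is enough.

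Protocol Appendix 2 needs no change; reflex microscopy is a reasonable testing rule. The cost is one SAP sentence and a line of programming, with no new data. The small downside is that a normal dipstick is accepted as no haematuria without a cell count, which a table footnote should state.
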